6.3 Exclusion Criteria

Subjects must not be enrolled into the study or randomly assigned to treatment if they meet any of the following exclusion criteria:

1. Currently enrolled, planning to enroll, or participated, within the last 30 days, in a clinical study requiring administration of an IP, including expanded access or compassionate use with the only exception being the administration of convalescent plasma. Administration of IP is permitted only if an emergency use authorization has been granted (eg, remdesivir). Additionally, off-label use of approved drugs (eg, anti-IL-6/anti-IL-6R) is also permitted.
2. Pregnant or breastfeeding (female subjects)
3. Intubated and require mechanical ventilation (including ECMO) at the time of randomization

4. In the opinion of the investigator, the subject is expected to be intubated in the first 24 hours after IP administration
5. Active Do-Not-Intubate (DNI) or Do-Not-Resuscitate (DNR) order
6. In the opinion of the investigator, not expected to survive for > 48 hours after admission
7. Presence of any of the following comorbid conditions prior to randomization and prior to SARS-CoV-2 infection:
 - Severe heart failure (New York Heart Association Class IV)
 - End-stage renal disease (Stage \geq 4) or need for renal replacement therapy
 - Biopsy-confirmed cirrhosis, portal hypertension, or hepatic encephalopathy
 - Malignancy (Stage IV)
 - Chronic lung disease requiring the use of oxygen at home
 - Active tuberculosis disease
8. Active bleeding or a current clinically significant coagulopathy (eg, international normalized ratio [INR] > 1.5) or clinically significant risk for bleeding (eg, recent intracranial hemorrhage or bleeding peptic ulcer within the last 4 weeks)
9. History of venous thrombosis, myocardial infarction, or cerebrovascular event within 3 months, or a prothrombotic disorder (eg, antithrombin III, protein C, or protein S deficiency)
10. Known or suspected Grade 3 or 4 infusion-related reaction or hypersensitivity (per Common Terminology Criteria for Adverse Events [CTCAE]) to monoclonal antibody therapy, or hypersensitivity to the IP or any excipients of the IP [[National Cancer Institute, 2009](#)]
11. Currently receiving a therapy not permitted during the study (see [Section 9.1](#))
12. Female subject of childbearing potential or fertile male subject either not using or not willing to use an acceptable method of contraception to avoid pregnancy during the study and for 90 days after receipt of the last dose of IP. Note: Acceptable methods of contraception are defined in [Section 9.3](#)

13. Any clinical or laboratory abnormality or other underlying conditions (eg, psychological disorders, substance abuse) that would render the subject unsuitable for participation in the study, in the opinion of the investigator

6.4 Discontinuation of Study Treatment and Subject Withdrawal

6.4.1 Early Discharge from the Hospital

All subjects who maintain consent will remain in the study through Day 28 for all important safety and efficacy assessments. All Day 28 assessments will be conducted on the day of discharge from the hospital. For subjects who are discharged before Day 28, the investigator (or delegate) will contact them via weekly telephone calls. If the telephone call is performed by non-medical study personnel, the information on clinical status, AEs, and changes in concomitant medications need to be reviewed by the investigator or a medically trained delegate. These subjects will be scheduled for an in-person visit on Day 28 to perform the End of Study (EOS) Visit assessments including CCI [REDACTED] and other laboratory parameters.

Every effort will be made to encourage both subject and investigators to continue study assessments via telephone following hospital discharge, unless the subject withdraws consent.

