### **8.2.5 Multiple Assessments**

All data will be reported according to the nominal visit date for which it was assessed (i.e., no visit windows will be applied during dataset creation and the visit will not be re-allocated if the actual visit date deviates from the planned date according to the visit schedule in the protocol). Unscheduled data will not be included in by-visit summaries, but may contribute to the Baseline value, the End of Study (EOS) value, or best/worst case value (e.g., shift tables) and will be displayed in the listings.

If multiple assessments on the same day or on different days are reported for the same scheduled visit, then the assessment for that scheduled visit will be analyzed according to the following rules:

- if an assessment was repeated as safety follow-up (e.g., laboratory value out of normal range) use the initial, abnormal assessment for that scheduled visit;

- in all other cases, use the last valid assessment for that scheduled visit; rationale: the assessment was repeated either because the initial assessment was missing or invalid (e.g., due to technical issues, loss of sample, clotting of sample or other reasons of this type) or the assessment was repeated but the reasons were not collected or unknown.

Data from all assessments (scheduled and unscheduled), including multiple assessments, will be included in the listings.

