### 12.1 Drug Concentration Measures

The handling and imputation of below limit of quantification (BLQ) values for PK parameter derivation is described in [PK-GDL-01](#). The imputation rules below will be used for summary statistics of CSL312 plasma concentrations. The summaries will be given by planned time point.

- The sampling time of pre-dose samples relative to start of the dose infusion will be treated as zero;
- Concentration values below BLQ in pre-dose samples and in samples taken before the time of the first quantifiable concentration will be treated as zero;
- Post-dose BLQ concentrations flanked by quantifiable concentrations will be set to missing;
- Post-dose BLQ concentrations after the last quantifiable point will be set to missing for summary statistics of plasma concentrations;
- The mean/median value at a time point where one or more samples have BLQ values will be reported (in tabular or graphical fashion) even if the mean/median value is BLQ of the assay;
- Zero mean or median values will be included in summary tables.

It should be noted that a high proportion of BLQ values may affect the summary statistics; if more than 50% of the values are imputed (i.e., BLQ), then the summary statistics (mean, SD, median, quartiles) will not be displayed.

Summary statistics for concentration-time data will include the percentage of BLQ values relative to the total N

$$\%BLQ = 100 * (\text{number of subjects who have BLQ values} / \text{total number of subjects})$$

at each time point.

Descriptive statistics will be provided as outlined in Section 7, and in addition the CV% and geometric mean.

Individual CSL312 plasma concentration plots (on log-linear scale) will be plotted versus actual sampling time. Multiple subject plots will be presented on 1 page.

Plots for mean ( $\pm$  SD) CSL312 plasma concentrations (on linear and on log-linear scales) versus nominal (planned) time will be provided. If more than 50% of the individual values are BLQ, the mean and SD will be set to missing in the plots.

Plasma concentrations excluded from the derivation of the PK parameters will also be excluded from the summary statistics and the mean plots. A footnote will indicate if plasma concentrations have been excluded from the analysis.

A by-subject listing of CSL312 plasma concentrations with the concentrations flagged that have been excluded from the derivation of the PK parameters based on the PK Analysis Set will support the summaries.

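### Assessments done at early discharge can be summarised as Day 28 values, because they carry the Day 28 label and the SAP applies no visit window

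*Protocol*

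**What the plan says.** Protocol 6.4.1 (Early Discharge from the Hospital) contains two instructions about the same set of assessments. The first is that "All Day 28 assessments will be conducted on the day of discharge from the hospital". The second concerns subjects who leave hospital before Day 28: "These subjects will be scheduled for an in-person visit on Day 28 to perform the End of Study (EOS) Visit assessments". Between the two dates, contact is by telephone: "For subjects who are discharged before Day 28, the investigator (or delegate) will contact them via weekly telephone calls".

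SAP 8.2.5 (Multiple Assessments) decides which record counts. The general rule is "All data will be reported according to the nominal visit date for which it was assessed", with the qualification that "no visit windows will be applied during dataset creation and the visit will not be re-allocated" when the actual date is off schedule. Where one scheduled visit has several records, on the same day or on different days, the default is to "use the last valid assessment for that scheduled visit". There is one exception: if the test was repeated as safety follow-up, the first, abnormal value is kept. Unscheduled data stay out of by-visit tables but may supply the End of Study value.

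For CSL312 concentrations, SAP 12.1 adds: "The summaries will be given by planned time point". Protocol 7.4 lists Day 28 as a scheduled PK sample.

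**The concern.** A subject discharged on Day 7 can have one Day 28 set dated Day 7 and, if the subject returns, a second one dated Day 28. Nothing in either document gives the first set a different name. If the subject does not return, the discharge-day set is the only Day 28 record, and no rule flags, relabels or excludes it.

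The affected values do not come from a random subset. They come from subjects who left hospital early, and the earlier the discharge, the larger the gap between the date of the value and its label. If treatment changes time to discharge, or if return rates differ by arm, the two arms' Day 28 summaries are affected unequally. At stake is the reading of the Day 28 rows and plots: clinical status on the NIAID scale with its improvement of at least 2 points (a named secondary endpoint), SOFA and its components, laboratory, vital signs, respiratory tests, and the nominal-time concentration profile.

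**Working it through.** The plan states no figure on this point, so there is none to reproduce. The check follows the rules in order and then sizes the consequence under stated assumptions.

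**Which record becomes Day 28**

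This assumes that the discharge set is stored under the nominal Day 28 visit.

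| Situation | Rule in SAP 8.2.5 | Value summarised as Day 28 |
|---|---|---|
| In-person visit attended, ordinary repeat | last valid record | true Day 28 value |
| In-person visit attended, Day 28 test counted as a safety repeat of an abnormal discharge value | initial abnormal record | discharge-day value |
| In-person visit missed | only one record, no window | discharge-day value |

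**Which analyses use that value**

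- Exposed, as far as each item is scheduled on Day 28: NIAID category and improvement by visit, and SOFA and components by visit (SAP 10.2.1); laboratory (SAP 11.3); vital signs (SAP 11.4.1); respiratory tests (SAP 11.4.2); concentrations by planned time (SAP 12.1).
- Not exposed: the primary endpoint (SAP 10.1), and mortality, intubation, CPAP/BiPAP, HFNC and ECMO (SAP 10.2), which all use dated records; and length of stay, which uses the discharge date.
- The tested SOFA quantities are each subject's maximum score, maximum change and mean. When the visit is missed, the label on a single record does not change them.
- C<sub>max</sub>, T<sub>max</sub>, AUC<sub>0-last</sub> and T<sub>1/2</sub> need not be affected, because SAP 12 supplies actual sampling times.

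**How many subjects**

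Let d be the share discharged before Day 28 and m the share of those who miss the in-person visit. Neither is in the documents; both are assumed. The affected share is d × m, applied to the planned 124 subjects (Protocol 11.1).

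- Low: 0.5 × 0.05 = 0.025, about 3 of 124.
- Middle: 0.7 × 0.20 = 0.14, about 17 of 124.
- High: 0.9 × 0.40 = 0.36, about 45 of 124.

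**NIAID example**

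The scale is scored at the first assessment of the study day (SAP 15.3), so a discharge-day score is normally an in-hospital score, 6 at most. A subject with baseline 4 who scores 5 that morning has improved by 5 − 4 = 1 point and does not meet the criterion. The same subject at home on Day 28 with a score of 7 has improved by 7 − 4 = 3 points and meets it.

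**Concentration example**

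Assume log-linear decline with half-life h days (not in the documents) and a sample taken on Day t but labelled Day 28. The value is too high by the factor F = 2^((28 − t)/h). If a share s of the values are affected and true Day 28 levels are otherwise alike, the nominal mean is multiplied by 1 + s(F − 1).

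| h (days) | t | F | s | Mean multiplied by |
|---|---|---|---|---|
| 21 | 7 | 2^(21/21) = 2.00 | 0.20 | 1.20 |
| 21 | 14 | 2^(14/21) = 1.59 | 0.20 | 1.12 |
| 21 | 21 | 2^(7/21) = 1.26 | 0.20 | 1.05 |
| 21 | 7 | 2.00 | 0.05 | 1.05 |
| 14 | 7 | 2^(21/14) = 2.83 | 0.20 | 1.37 |
| 28 | 7 | 2^(21/28) = 1.68 | 0.20 | 1.14 |

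At the central half-life, the nominal Day 28 mean is therefore between about 5% and 20% too high over these cases.

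**The case against.** The strongest reply is that the mechanism depends on documents outside the text. The Schedule of Assessments grid, the eCRF and the table shells are not available. If the eCRF has its own discharge page, or if the set is entered as unscheduled, SAP 8.2.5 keeps it out of the by-visit tables, though as unscheduled data it could still supply the End of Study value. This stands as a condition on the point. It does not remove it, because the Protocol calls the set the Day 28 assessments and the SAP defines no discharge visit.

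Second, the design largely repairs itself: each subject discharged early is to be seen in person on Day 28, and the last-valid rule then normally picks that value. This also stands, except for safety repeats. What remains is mainly missed visits, whose frequency is unknown. For NIAID, a telephone contact could supply Day 28 status, so even a missed visit need not leave the discharge score in place.

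Third, SAP 10.3 declares every test but the primary one descriptive, assessment dates remain visible in the listings, and individual concentration plots use actual time. That is correct and limits the harm to how summary tables and mean plots are read.

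A reader might infer that the primary result, the event endpoints or the PK parameters are biased. The documents do not support that: the first two rest on dated records, and actual sampling times are available for the third. PK summaries also cover only CSL312-treated subjects, so they contain no comparison between arms to distort. A reader might also take the 20% rise in the concentration mean as typical. It is one corner of a range, with discharge on Day 7 and one subject in five affected.

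**Conclusion.** The point holds in a conditional and limited form. On the plain wording, the Day 28 summaries can contain discharge-day values when the in-person visit is missed. They can also do so when the visit is attended, if the Day 28 test is treated as a safety repeat of an abnormal discharge value. This follows from the stated rules taken together and is not merely a missing detail. It assumes that the discharge set is filed under nominal Day 28.

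Its reach is the descriptive by-visit and nominal-time summaries. The by-visit NIAID improvement is the most consequential of these, because there the substitution can turn a subject who meets the criterion into one who does not. No overall size can be fixed, since the documents give no discharge pattern, return rate or half-life; the ranges worked above are illustrations. It would go too far to say that early-discharge values are known to enter Day 28, or that they do so after every missed visit. The point is worth correcting because the correction is cheap; it does not threaten the trial's main conclusion.

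**What to change.** - Reconcile the two sentences in Protocol 6.4.1, so that it is clear which assessments belong to discharge and which to Day 28.
- Record discharge-day assessments under a separate Discharge visit. If the eCRF cannot be changed, derive that label from the assessment date and the recorded discharge date, and state this as an exception to the no-re-allocation rule in SAP 8.2.5.
- State in SAP 8.2.5 that Discharge values are not summarised as Day 28 (unless discharge itself falls within the Day 28 window), and that the initial-abnormal-value rule does not apply between the Discharge and Day 28 visits.
- Set a window around Day 28, and use only assessments inside it for Day 28 by-visit and nominal-time concentration summaries.
- For NIAID, accept Day 28 status obtained by telephone within that window.
- Report the number of subjects missing at Day 28 by arm.

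The cost is some SAP and Protocol wording, one visit label and slightly fewer Day 28 values. The change does not remove selection: subjects who do not return, who may be early recoverers, will now be absent from the Day 28 tables instead of mislabelled in them. This is why the count of missing subjects by arm should be shown next to those tables.

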6.4.2 Discontinuation of Study Treatment

Subjects may discontinue study treatment with the IP at any time at their own request, or at the discretion of the investigator or CSL for safety, behavioral, or administrative reasons.

Subjects who discontinue treatment with the IP but remain in the study, will be asked to complete additional follow-up assessments or allow data collection as detailed in the Schedule of Assessments. If a subject discontinues IP and declines further study procedures/visit participation, the subject will be withdrawn from the study, and attempts will be made to complete and document the EOS Visit assessments.

6.4.3 Subject Withdrawal

Subjects may withdraw from the study at any time either at their own request or at the discretion of the investigator or CSL for safety, behavioral, or administrative reasons (eg, because of an AE, protocol deviation, subject noncompliance, or study termination). The investigator should record in the electronic case report form (eCRF) and in the subject's medical records the reason for and date of subject withdrawal.

In accordance with the ICH principles of Good Clinical Practice (GCP), the investigator always has the option to advise a subject to withdraw from the study if the subject's safety or well-being is compromised by his or her further participation in the study. Concern for the interests of the subject must always prevail over the interests of the study.

6.4.4 Procedures for Handling Withdrawals

If a subject is withdrawn from the study, attempts will be made to complete and document the Day 28 (EOS) Visit assessments. If the subject is withdrawn from the study after receiving IP, every effort will be made to ensure that the relevant safety assessments are completed. The subject may also be asked by the investigator to complete other study assessments.

If the subject withdraws from the study, and also withdraws consent for disclosure of future information, CSL may retain and continue to use any data collected before such withdrawal of consent.

6.4.5 Replacement Policy

Subjects withdrawn from the study will not be replaced.

7 Study Assessments

7.1 Unscheduled Study Assessments and Additional Medical Data

Unscheduled study assessments are possible and can be documented in the unscheduled visit in the eCRF.

Additional data given to CSL may include any medical information from hospital records required by the study but not outlined in the study protocol. This information may be required to help scientific understanding of study data and might be collected even the completion of the study.

7.2 Efficacy Assessments

Outcome assessments will include the following:

- Use of supplemental oxygen
- Use of CPAP or BiPAP
- Use of HFNC
- Use of ECMO
- Intubation
- Extubation
- Clinical status on standardized scales (SOFA score and NIAID 8-point ordinal scale score)
- ICU admission and discharge
- Hospital discharge or death

7.3 Demographics and Safety Assessments

The clinical procedures to be conducted during this study related to the evaluation of safety are provided in Table 3. Some laboratory assessments may also be used for Screening. Clinical laboratory assessments are to be performed at time points as detailed in the [Schedule of Assessments](#).

Table 3 Demographics and Safety Assessments

Assessment	Description
Demographics	
 • Year of birth/age • Sex • Race and ethnicity
Medical History	
 • Relevant medical history • Contraception method (if relevant) • Previous and concomitant medications and therapies • Smoking history
Pregnancy Test (local laboratory)	
 • Urine test for β-hCG will be performed for all female subjects of childbearing potential to rule out pregnancy at Screening and the end of the Treatment Period. A serum pregnancy test will be performed by the site if urine result is inconclusive.
Physical Examination	
 • As per the study site's standard procedure
Chest CT scan or X-ray	
 • Chest CT scan or X-ray results must show signs of interstitial pneumonia to confirm eligibility criteria at Screening.

Assessment	Description
Adverse Events	
 • Evaluation of all AEs (eg, causality/relatedness, severity, seriousness) • AESIs: 
 ○ Abnormal bleeding events ○ TEEs ○ Severe hypersensitivity including anaphylaxis
Vital Signs	
 • Blood pressure (systolic and diastolic) • Heart rate • Body temperature • Height and weight
Respiratory Parameters	
 • Respiratory rate • SpO₂ • FiO₂ • PaO₂
Urinalysis (dipstick) (test kits provided for local laboratory)	
Mandatory review of all parameters indicated by * is required before randomization.
 
 • Specific gravity • pH • Leukocyte esterase* • Occult blood* • Nitrite • Ketones • Bilirubin • Urobilinogen • Protein* • Glucose*
Hematology (local laboratory)	
Mandatory review of all parameters indicated by * is required before randomization.
 
 • Hemoglobin* • Hematocrit* • Erythrocytes (RBC count)* • RBC indices: mean corpuscular volume; mean corpuscular hemoglobin; mean corpuscular hemoglobin concentration; erythrocyte distribution width • Platelets* • Leukocytes (WBC count)* • WBC differential (percentage or absolute): neutrophils; neutrophil band forms; lymphocytes; monocytes; eosinophils; basophils • Reticulocytes

Assessment	Description
Biochemistry (local laboratory)	
Mandatory review of all parameters indicated by * is required before randomization.
 
 • Sodium* • Potassium* • Chloride* • Bicarbonate • Carbon dioxide • Calcium • Blood urea nitrogen* • Urea* • Creatinine* • Glucose* • Total protein • Albumin • Alkaline phosphatase* • ALT* • AST* • GGT* • LDH* • Total bilirubin* • Direct bilirubin* • Magnesium* • Phosphate • CRP* • Total cholesterol • Triglycerides • HDL cholesterol • LDL cholesterol • Uric acid • CK, CPK* • Ferritin
Coagulation (central laboratory)	
 • CCI • CCI
Coagulation (local laboratory)	
 • CCI • CCI
PK assessments (central laboratory)	
 • C_{max} • T_{max} • AUC_{0-last} • T_{1/2}
Cytokine Profile (central laboratory)	
 • Inflammatory cytokine panel
CCI (central laboratory)	
 • CCI

CCI; AESI = adverse events of special interest; ALT = alanine aminotransferase; CCI; AST = aspartate aminotransferase; AUC_{0-last} = area under the plasma concentration-time curve from time zero to the time of the last measureable concentration; β-hCg = beta-human chorionic gonadotropin; BUN = blood urea nitrogen; CK/CPK = creatine kinase; C_{max} = maximum plasma concentration; CRP = C-reactive protein; FiO₂ = fraction of inspired oxygen; GGT = gamma-glutamyl transferase; HDL = high-density lipoprotein; INR = international normalized ratio; LDH = lactate dehydrogenase; LDL = low-density lipoprotein; PaO₂ = partial pressure of arterial oxygen; PT = prothrombin time; RBC = red blood cell; SpO₂ = saturation of peripheral (capillary) oxygen; T_{1/2} = terminal half-life; TEE = thromboembolic event; WBC = white blood cell.

